	Screening	Run-In Period	Baseline	Treatment Period	End of Treatment	Washout Period	Notes
Study Days	-30 to -1	-18 to -5	-3 to 0	1 to 28	28	29-56	
Window	0	±3 days	±1 day	+4 days	+ 4 days	+4 days	
Informed consent	X						Prior to any study procedures
Inclusion/exclusion criteria	X		X				
Demographic information and medical history	X						
Prior and concomitant medication	X	X	X	X	X		
Physical Exam	X				X		Exam may be delayed if remote consenting
Randomization		X					After completion of screening assessments
Rectal Compliance and Sensation study			X		X		
Pregnancy test if required	X		X		X		Prior to baseline assessments and radioisotopes
Gastric and colonic transit study			X		X		
Talley Bowel Questionnaire	X						
Daily Abdominal Pain Score by VAS	X	X	X	X	X	X	
Daily Bowel Diary including Bristol Stool Form Scale	X	X	X	X	X	X	
IBS Quality of Life Questionnaire	X				X	X	
Hospital Anxiety Depression Questionnaire	X				X	X	
Adverse Events				X	X	X	Recorded from study day 1 through washout period
Study drug administration				X	X		Administered every other day through the end of treatment assessments
Dispense study drug			X				

STUDY PARTICIPANTS

Twenty-four participants with non-constipation IBS and chronic abdominal pain will be recruited for enrollment. Participants will meet specific Rome III IBS diagnostic criteria.

The rationale for NOT using Rome IV criteria stems from the evidence in the literature that documented that the Rome IV criteria actually select participants with higher psychological or psychiatric burden and higher pain severity that may be more appropriate for a central neuromodulator or antidepressant approach. This experience has been documented in studies from Europe, North America and China.³⁶⁻⁴⁰

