Note the methacrylate-coated capsule dissolves in the alkaline pH of the distal ileum to release ¹¹¹In-labeled activated charcoal particles to evaluate colonic transit on sequential scans.⁴⁷ In this study we propose to measure only colonic transit in the participants with non-constipation IBS.

Colonic geometric center (GC, weighted average of isotopic counts) in colon at 4, 24 and 48 hours provide excellent summaries of colonic transit with similar diagnostic accuracy as more detailed, costly, and time-consuming analyses.^{48,49}

Data obtained in patients with IBS are summarized from a study of almost 300 patients.⁵⁰

$$(\%AC \times 1 + \%TC \times 2 + \%DC \times 3 + \%RS \times 4 + \%stool \times 5) = GC$$

	IBS-C/FC	IBS-D/FD	IBS-M	Healthy Controls
Colonic GC 24**	2.0 ± 0.1	3.2 ± 0.1	2.3 ± 0.1	2.4 ± 0.1
(n=453)	(n=118)	(n=138)	(n=30)	(n=167)
Colonic GC 48**	3.0 ± 0.1	4.3 ± 0.1	3.9 ± 0.2	3.6 ± 0.1
(n=411)	(n=118)	(n=112)	(n=30)	(n=151)

Rectal Compliance and Sensation by Barostat

An established and validated method using rectal barostat device will be used to measure rectal compliance and sensation.⁵¹

After completing the 48 hour scan that completes the colonic transit measurement, all study participants will undergo the rectal compliance and sensation test. A rectal catheter with a polyethylene bag attached (length 22 cm; capacity 600 ml) will be inserted into the rectum so that the middle of the balloon is located approximately 10 cm from the anal verge. After a 5 minute recovery period, the catheter will be connected to a barostat (G&J Electronics Inc., Toronto, Ontario, Canada) and the bag will be unfolded by inflation with 75 ml of air, followed by complete deflation. After a 10 minute recovery period, to decrease the effects of abdominal viscera on the balloon volume, the participants will be placed in a semi-prone position and the foot end of the bed elevated 15 degrees. An initial "conditioning" distension of the rectum will then be performed in which the pressure is increased from 0 mmHg in steps of 4 mmHg for 15 seconds per step until 20 mmHg was reached. This "conditioning" distension to 20 mmHg renders subsequent assessments of compliance and perception more reproducible.⁵¹ The bag is then deflated to 0 mmHg and the participants are allowed to rest for 10 minutes before proceeding to the ascending method of limits. During this rest, the VAS of "tiredness", "peace", "worried", and "activity" scores will be collected.

[figure not shown]

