The covariates to be considered for inclusion in the ANCOVA models for colonic transit are gender, BMI, HAD scores (anxiety and depression scales), the BDQ Somatic Symptom Checklist (SSC) score. These will be considered for inclusion by checking plots of residuals (from the ANCOVA models) against these scores. The analysis will compare colonic transit between the two treatment groups.

Gastric Emptying

Given the reports of nausea and vomiting in participants with migraine as well as observations of these symptoms during clinical trials of CGRP receptor antagonists, we will also measure gastric emptying $T_{1/2}$ (minutes) and proportion emptied at 4h (%) at the end of 4 weeks treatment and compare the results for the active treatment group to those of the placebo group. Sex and BMI will be considered as co variates in this analysis.

Sensory Ratings

The assessment of phenotype associations with observed sensory ratings (rectal sensation VAS scores) will be based on analysis of covariance (ANCOVA) for repeated measures (the four phasic distension levels). Each type of VAS score will be analyzed individually (first sensation, gas, urgency, and pain). The covariates to be included in the ANCOVA models for each VAS score were age, sex, BMI, the “tiredness”, “peace”, “worried”, and “activity” VAS scores, the HAD scores, and the BDQ SSC score. Though most of these scores may not be significant covariates in these models, due to the nature of the responses, it is appropriate to include them. In addition, the corresponding pressure (12, 24, 30, 36 mmHg) at each phasic distension level (the repeated factor) is included in each of these ANCOVA models along with the main effect term for phenotype (e.g. age, sex, BMI), and the 2-way interaction term for phenotype by pressure.

Sensation pressure thresholds

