Radiation exposure in this study involves radiation exposure from the ¹¹¹In used to measure colonic transit. These exposures conform to previously approved levels of radiation exposure approved by the Radiation Control Committee at Mayo Clinic. The radiation dosimetry and organ exposures (in mrad) are listed below.

GASTROINTESTINAL AND COLONIC TRANSIT TESTS

Radiopharmaceutical	Act mCi	Body	Gonads	Breast	Red marrow	Lung	Thyroid	Bone	ULI	Colon	Stom	Blad	Liv	Esoph	Other
											-ach	-der	-er	-agus	
¹¹¹ In charcoal	0.10	20	140		20				380	740	60	40	10	160	
^{99m} Tc-sulfur colloid	1.0	20	90		20				420	300	130	20	10	220	

(mrad= unit of radiation absorbed dose to organs)

H_e or the radiation effective dose to the body summarizes the risk to the whole body as the individual doses to each of the organs; effective dose is used to compare risks among various types of x ray and radionuclide studies: ¹¹¹In Cl₃ 0.1 mCi : H_e 142 mrem (where mrem= radiation equivalent dose); ^{99m}Tc sulfur colloid 1.0 mCi, H_e = 90 mrem; note that participants will receive ¹¹¹In on 2 occasions separated by about 1 month

In view of the radiation exposure, all females of childbearing age will be required to have a negative urine pregnancy test within 48 hours of performance of fluoroscopy or the radioisotope studies.

Significance of the Proposal

Rimegepant, at doses and mode of administration approved by FDA for the prophylaxis of migraine headache, will be efficacious in the reduction of abdominal pain and rectal sensation in participants with non-constipation IBS and abdominal pain.

This study will provide preliminary data to support the calculation of the variance in response and therefore plan a future controlled trial.

Gender/Minority Mix

All efforts will be made to recruit participants of both genders, and of diverse ethnicity.

HUMAN STUDIES PROTECTION

I. CONFIDENTIALITY

Mayo Clinic upholds the most stringent standards for protection of human subjects and privacy while balancing the crucial importance of data sharing to advance medical science. This is applied to all patients participating in research activities, direct care and as study participants. Protection of privacy is assured based on Mayo Clinic's standards and procedures, including rules in full compliance with current HIPAA regulations. All staff members are trained in privacy compliance and held to the strictest standards.

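### The radiation text counts only In-111 doses, and the protocol's sections disagree on whether gastric emptying (and with it Tc-99m) is done at zero, one or two visits

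*Combined protocol and SAP*

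**What the plan says.** The radiation paragraph under Potential Risks opens by naming one source: "Radiation exposure in this study involves radiation exposure from the ¹¹¹In used to measure colonic transit". It then says that the exposures conform to levels already approved by the institution's Radiation Control Committee. The dosimetry table that follows, headed "GASTROINTESTINAL AND COLONIC TRANSIT TESTS", has two rows: In-111 charcoal (0.10 mCi) and Tc-99m sulfur colloid (1.0 mCi), each with organ doses. The note below the table gives an effective dose for each isotope: "¹¹¹In Cl₃ 0.1 mCi : H_e 142 mrem" for In-111, and 90 mrem for 1.0 mCi of Tc-99m. It closes with a count for In-111 alone: "participants will receive ¹¹¹In on 2 occasions separated by about 1 month". There is no count for Tc-99m and no sum.

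Elsewhere the protocol describes the transit tests as follows.

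- **Schedule of Assessments:** the row "Gastric and colonic transit study" is marked at Baseline and at End of Treatment.
- **Study Design, Baseline:** only colonic transit is named among the transit tests.
- **Methods for Physiological Endpoints, Colonic transit:** "In this study we propose to measure only colonic transit in the participants with non-constipation IBS".
- **Statistical Analysis, Gastric Emptying:** half-time and proportion emptied at 4 h are to be measured "at the end of 4 weeks treatment and compare the results for the active treatment group" with those of placebo. Sex and BMI are the only covariates considered.
- **Endpoints:** gastric emptying half-time and percent emptied at 4 h are secondary endpoint c. The Sample Size table gives a detectable effect for each.

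**The concern.** Someone who reads the radiation narrative alone would take the exposure to be two In-111 administrations. Someone who reads the Schedule would expect a gastric study at both visits as well, and the only other radiopharmaceutical in the dosimetry table is Tc-99m. The protocol does not say which description governs.

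Two things depend on the answer. The first is the cumulative dose. The statement that exposures conform to approved levels comes directly after the sentence naming In-111 alone, so a reader cannot tell whether it covers no Tc-99m dose, one or two. The second is the analysis of a secondary endpoint. If gastric emptying is measured at both visits, a baseline value exists and the stated analysis makes no use of it. If it is measured only at the end, no baseline value exists. If it is not measured at all, secondary endpoint c has no data.

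**Working it through.** The plan states no cumulative dose, so there is no figure of its own to reproduce. The check has two steps: count the gastric studies that each section implies, then convert the counts to effective dose with the protocol's own figures per administration.

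**Inputs (Potential Risks, radiation paragraph)**

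- In-111: 142 mrem per administration, 2 administrations.
- Tc-99m sulfur colloid: 90 mrem per administration, number of administrations *k* not given.

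**Which tracer the gastric study uses.** No section says outright that gastric emptying is traced with Tc-99m. The inference is strong. The Colonic transit section describes the In-111 charcoal as held in a coated capsule that opens only when it reaches the distal ileum, so it cannot trace emptying of the stomach. Tc-99m is the only other isotope listed.

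**Formula.** Total effective dose = 2 × 142 + *k* × 90 mrem.

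| Section | Gastric studies implied (*k*) | Total | Relative to In-111 alone |
|---|---|---|---|
| Colonic transit methods | 0 | 2 × 142 = 284 mrem | reference |
| Gastric Emptying analysis; secondary endpoint c | at least 1 | 284 + 90 = 374 mrem (at *k* = 1) | 374/284 = 1.317, or +32% |
| Schedule of Assessments | 2 | 284 + 2 × 90 = 464 mrem | 464/284 = 1.634, or +63% |

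Study Design names only colonic transit at baseline. That fits *k* = 0, or *k* = 1 with the single study at the end of treatment. It does not fit the Schedule's baseline mark.

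**How the counts compare.** Zero is the hardest to reconcile with the rest, because gastric emptying has an endpoint entry, an analysis and two rows in the Sample Size table. One and two are closer. The Gastric Emptying section places the measurement at the end of treatment but does not exclude a baseline study.

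**Consequence for the analysis.** With 12 participants per arm, a covariate that correlates with the outcome at ρ reduces the residual standard deviation by a factor of about √(1 − ρ²), less a small cost in degrees of freedom. The documents give no baseline-to-follow-up correlation for gastric emptying, so the gain cannot be quantified here. If the Schedule stands, the baseline measurement is already being made, and using it requires no further procedure.

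**The case against.** A reader might infer that the protocol states an exposure of 284 mrem and understates the true figure by 63%. The documents do not support that, for four reasons.

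- The radiation text does not leave Tc-99m out. It prints the organ doses and the 90 mrem effective dose.
- No total is stated, so no stated total can be too low. The figures 284, 374 and 464 are all derived here.
- The 464 mrem figure holds only if the Schedule is the operative text. Measured from one Tc-99m dose, the difference is smaller: 464/374 = 1.24, or 24%.
- Tc-99m as the gastric tracer is an inference. The figure showing the scintigraphic method is not reproduced in the available text and may label the tracers.

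It can also be said that the Gastric Emptying section and the Schedule are compatible, since comparing groups at the end of treatment does not rule out a baseline study. Harm to participants cannot be shown either, because the consent pages and the committee's approval are not in the file.

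All of these points stand, and they limit the finding. They do not remove the conflict between the methods sentence that restricts measurement to colonic transit and the three places that schedule, analyse or list gastric emptying. Nor do they supply the missing Tc-99m count or explain why the narrative names In-111 alone.

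**Conclusion.** The point holds as an internal inconsistency. The protocol's sections imply zero, at least one, or two gastric studies, and the radiation narrative names and counts only In-111 while its own table lists a second isotope with no number of administrations. On the protocol's figures per dose, the cumulative effective dose ranges from 284 to 464 mrem per participant, a spread of 180 mrem.

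That range assumes two In-111 administrations, as stated, and one listed Tc-99m dose per gastric study, as inferred. No calculation in the protocol is wrong. The documents do not show that the approved exposure is exceeded or that participants are misinformed. What they show is that neither the total exposure nor the existence of a baseline gastric value can be determined from the text.

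**What to change.** 1. Reconcile Study Design, the Schedule of Assessments, the Colonic transit methods, the Gastric Emptying analysis, the Endpoints list and the radiation paragraph on whether and when gastric emptying is measured. Which schedule applies is for the investigators.
2. Correct the sentence that attributes exposure to In-111 alone if Tc-99m is given. Name the tracer used for gastric emptying.
3. State the number of Tc-99m administrations and the matching total effective dose per participant, and confirm that the Radiation Control Committee's approval covers that total.
4. If the Schedule's baseline gastric study stands, add the baseline value of each gastric emptying measure as a covariate in its analysis, alongside sex and BMI. If there is no baseline study, say so in the analysis section and remove the gastric component from the Schedule's baseline column.

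The cost is wording, plus one check with the committee. Item 4 needs no additional data if the baseline study is already planned. The stated exposure will look less favourable than the present narrative if Tc-99m is given.

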Each participant will be carefully monitored for the development of any adverse events. All adverse events (serious and non-serious) spontaneously reported by the patient and/or in response to an open question from study personnel or revealed by observation, physical examination or other diagnostic procedures will be recorded on the appropriate page of the CRF. Any clinically relevant deterioration in laboratory assessments or other clinical findings is considered an adverse event and must be recorded on the appropriate pages of the CRF. When possible, signs and symptoms indicating a common underlying pathology should be noted as one comprehensive event.

Unexpected, serious, and/or intervention-related SAEs will be reported to the independent monitor, IRB, CRTU, and Pfizer within 24 hours of the institutional awareness or immediately if fatal or life-threatening.

Anticipated or unrelated SAEs will be reported to the independent monitor (as in the DSMP), IRB, CRTU, and Pfizer within 24 hours of the institutional awareness. In the annual SAE summary, the independent monitor shall state that he has reviewed all adverse reports.

The investigator will promptly notify the IRB of all unexpected serious adverse drug reactions involving risk to human subjects. An unexpected event is one that is not reported in the Physicians' Desk Reference manual regarding the study drugs.

Exposure during pregnancy and lactation are reported independently from any associated SAE. Medication errors and overdoses are reportable only if associated with an SAE.

Occupational/environmental exposure is reported independently from any associated AE/SAE. Lack of Efficacy is reportable only if associated with an SAE.

Cases of potential drug-induced liver injury as assessed by laboratory test values ("Hy's Law Cases") are reportable SAEs. If a Study subject develops abnormal values in aspartate transaminase ("AST") or alanine transaminase ("ALT") or both, concurrent with abnormal elevations in total bilirubin and there is no other known cause of liver injury, that event would be classified as a Hy's Law Case.

For both serious and non-serious adverse events, the investigator will determine both the intensity of the event and the relationship of the event to study drug administration.

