The **intensity of all adverse events**, including clinically significant treatment-emergent laboratory abnormalities, and potential systemic reactions, will be graded according to the National Cancer Institute **Common Terminology Criteria for Adverse Events** (CTCAE) Version 5.0. The CTCAE grade refers to the severity of the adverse event and ranges from Grade 1 (mild), Grade 2 (moderate), Grade 3 (severe) and Grade 4 (life-threatening or disabling) to Grade 5 (death related to adverse event).

Adverse events not listed in the CTCAE (e.g., physical signs or symptoms) will be classified as follows:

- **Mild:** discomfort noticed; no disruption of normal daily activity; no major impact on patient
- **Moderate:** discomfort sufficient to reduce or affect daily activity; causes minor inconvenience
- **Severe:** inability to work or perform normal daily activity; causes a substantial disruption to the patient's wellbeing
- **Life threatening:** represents an immediate threat to life

Relationship of Adverse Events to Study Procedure

	The PI will determine the relationship of AEs to the test procedure/device/agent as definitely related, probably related, possibly related, unrelated, or unknown.
	
The PI will use an alternative attribution scale (specify):
 
 • None: No relationship between the event and the study procedure. The event is related to other etiologies, such as concomitant medications or subject's clinical state. • Unlikely: The current state of knowledge indicates that a relationship to study procedure is unlikely or the temporal relationship would not have had any reasonable association with the observed event. • Possible: A reaction that follows a plausible temporal sequence from the study procedure and follows a known response pattern to the procedure. The reaction might have been produced by the subject's clinical state or other modes of therapy administered to the subject. • Probable: A reaction that follows a plausible temporal sequence from the study procedure and follows a known response pattern to the procedure and cannot be reasonably explained by the known characteristics of the subject's clinical state or other modes of therapy administered to the subject.

For the purpose of safety analyses, all adverse events that are classified as possible or probable will be considered treatment-related events.

REFERENCES

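### Both grades that count as treatment-related require a known response pattern, so a well-timed reaction of a new kind cannot enter the treatment-related count

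*Combined protocol and SAP*

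**What the plan says.** The section on the relationship of adverse events offers two scales. The unticked one grades events as "definitely related, probably related, possibly related, unrelated, or unknown". The ticked one has four grades: None, Unlikely, Possible and Probable.

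- 'Possible' begins: "A reaction that follows a plausible temporal sequence from the study procedure and follows a known response pattern to the procedure". It allows that the participant's condition or other treatment might also be the cause.
- 'Probable' needs the same timing, and the event must be one that "follows a known response pattern to the procedure and cannot be reasonably explained by the known characteristics of the subject's clinical state" or by other treatment.
- 'Unlikely' applies where "The current state of knowledge indicates that a relationship to study procedure is unlikely", or where the timing does not fit.
- 'None' applies where the event has another cause.

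The section ends with the rule for analysis: "For the purpose of safety analyses, all adverse events that are classified as possible or probable will be considered treatment-related events".

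The preceding section, on reporting procedures, says that "the investigator will determine both the intensity of the event and the relationship of the event to study drug administration". It requires prompt notice to the IRB of serious drug reactions that were not expected, and adds: "An unexpected event is one that is not reported in the Physicians' Desk Reference manual regarding the study drugs".

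**The concern.** The two grades that count share one condition: the reaction must already be known. A reaction of a new kind fails that condition however good its timing, and even if no other cause can be found. The reporting section nevertheless assumes that an investigator can recognise a drug reaction that was not expected.

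Safety is part of the study hypothesis, secondary aim 4 and a listed secondary endpoint. The Introduction states that the effects of gepants on transit, rectal sensation and abdominal pain in non-constipation IBS are not known. A pilot in such a population should be able to show reactions not yet described. The rule quoted above is also the only sentence in the document on how adverse events enter an analysis. The STATISTICAL ANALYSIS section specifies no comparison of adverse events by arm, so the treatment-related count may become the main safety summary by default.

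**Working it through.** The plan gives no figure on this point, so there is none to reproduce. The check is to apply the definitions to one event, followed by simple arithmetic for scale.

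**Step 1. Grade one event.** Take an event with plausible timing, no other apparent cause, and no known pattern.

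| Grade | What it requires | Met? | Counts as treatment-related? |
|---|---|---|---|
| None | Another cause | No | No |
| Unlikely | Knowledge pointing against a link, or timing that does not fit | No: absence of knowledge is not knowledge against, and the timing fits | No |
| Possible | Plausible timing and known pattern | No: second part fails | Yes |
| Probable | Plausible timing, known pattern and no other explanation | No: second part fails | Yes |

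No grade fits. The text does not say where the event goes, but it meets neither of the definitions that count. The unticked scale has an 'unknown' level and no known-pattern condition; the chosen scale has neither feature.

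**Step 2. Direction.** Under Blinding, investigators do not know the arm, so the same rule acts on both arms. A reaction truly caused by the drug arises in the active arm, so leaving it out moves the active related count towards that of placebo.

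**Step 3. Scale.** The arm size is 12 (Sample Size). The true rate p of a new reaction is an assumption. With at most one event per participant:

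- expected events left out of the active related count = 12 × p
- chance that at least one occurs = 1 − (1 − p)^12

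| Assumed p | 12 × p | Chance of at least one |
|---|---|---|
| 5% | 0.6 | 1 − 0.95^12 = 46% |
| 10% | 1.2 | 1 − 0.90^12 = 72% |
| 20% | 2.4 | 1 − 0.80^12 = 93% |
| 30% | 3.6 | 1 − 0.70^12 = 99% |

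Under the literal rule the related count for such a reaction is 0 in every row. The expected numbers are upper values, because they take every occurrence to be well timed and gradable as 'Possible' once the condition is removed. The all-cause count is the same with or without the condition.

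**Step 4. What a zero would mean.** Even a correct 0 of 12 is compatible with a rate of up to 1 − 0.05^(1/12) = 22.1% (one-sided 95% limit), or 1 − 0.025^(1/12) = 26.5% (two-sided 95% interval).

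**The case against.** The strongest reply is that the closing rule only defines a label. It does not limit the safety analysis to labelled events. All adverse events go on the case report form whatever their grade, and the Schedule of Assessments collects them from day 1 through washout. Serious events reach the monitor, the IRB and the company within 24 hours even if judged unrelated. The endpoint is listed as safety and adverse effects, not as related events. All of this stands, and it confines the problem to the treatment-related count.

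A second reply is that absence from one reference manual is not absence of any known pattern. This also stands. The Introduction itself draws on other knowledge, such as case reports of Raynaud's phenomenon and a mechanism for constipation. An investigator may read the known-pattern phrase broadly, so the effect in practice may be smaller than the literal text implies.

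A third reply is that the scale is worded for the study procedure while the reporting section asks about the drug, so the definitions need rewriting in any case. That is true, but replacing 'procedure' with 'drug' leaves the known-pattern condition in both grades. Blinding does not remove it either.

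Three stronger readings are tempting and are not supported:

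- **The whole safety result is biased towards 'safe'.** All-cause counts and serious-event reporting do not depend on the grade.
- **Every event missing from the manual drops out.** Only a reaction with no known pattern from any source is affected, and only under a strict reading.
- **A reported 0 of 12 would rule out a true rate such as 25%.** That rate is invented, the conclusion holds for the one-sided limit (22.1%) but not the two-sided one (26.5%), and the plan specifies no such interval.

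**Conclusion.** The point holds in a limited form. Followed as written, the scale cannot classify a well-timed reaction without a known pattern as treatment-related. That is a fault in a stated rule, and it does not agree with the reporting section's expectation of drug reactions that were not expected. The consequence is a possible understatement of the treatment-related count in the active arm.

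Its size cannot be taken from the documents. At assumed true rates of 5% to 30% it is about 0.6 to 3.6 expected events among 12 treated participants. This rests on a strict reading of the known-pattern condition and on the assumption that such reactions would otherwise be graded 'Possible'. It is worth correcting because the treatment-related rule is the only analysis rule for safety in the text.

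**What to change.** 1. Define 'Possible' by plausible timing, whether or not a known pattern exists, keeping the allowance for other contributing causes. The condition may remain in 'Probable', because 'Possible' is enough for an event to be counted.
2. Word the scale for the study drug, so that it agrees with the attribution asked for in the reporting section. If attribution to study procedures is also wanted, grade it separately.
3. Replace the closing rule with a statement that all treatment-emergent adverse events are tabulated by randomised arm regardless of attribution, with possible and probable events shown second.

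The cost is a few sentences of protocol text and one line of guidance for the case report form. No new data are needed. The downside is that somewhat more events will be labelled 'possible' in both arms, which is why the all-cause table should come first.
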